- The principal investigator of this study is qualified to serve as P.I. and has the support of the hospital for this research project.

YNHH HSPA Name (PRINT) and Signature _____

Date _____

For HIC Use Only

Date Approved _____

Human Investigation Committee Signature _____

This protocol is valid through _____

SECTION V: RESEARCH PLAN

1. **Statement of Purpose:** State the scientific aim(s) of the study, or the hypotheses to be tested.
Specific Aims:
1. Determine the incidence of prostate cancer in men with the BRCA2 gene mutation as an independent indicator for prostate cancer screening.
2. **Background:** Describe the background information that led to the plan for this project. Provide references to support the expectation of obtaining useful scientific data.

Prostate cancer remains the most commonly diagnosed malignancy among men with an estimated 230,000 incident cases annually in the U.S. Emphasis has been placed on overtreatment, but prostate cancer remains the most lethal malignancy for men. Genetic factors, like a family history of prostate cancer, are associated with a higher risk of developing the disease, but a connection with more aggressive disease is controversial. Recently, the BRCA mutation, commonly known for its role in breast and ovarian cancer, has been identified as risk factor for prostate cancer in men that may also confer a risk of developing more aggressive prostate cancer at a younger age. While several retrospective studies of men with prostate cancer suggest that BRCA2 mutation carriers are at significantly higher risk of developing prostate cancer at an earlier age and more advanced stage, [1-4] prospective data is lacking. Concern about whether this mutation confers more advanced disease and worse survival may contribute to significant anxiety in some men. A man in England with a BRCA2 mutation, for example, was so worried about his possible risk of prostate cancer that he had a

prophylactic surgical removal of his prostate[5]. This example clearly illustrates the key knowledge gaps that exist about the actual risk of prostate cancer among BRCA2 mutation carriers.

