We have established a multidisciplinary group of radiation oncologists, urologists, geneticists and engineers that is uniquely positioned to address this knowledge gap about the importance of the BRCA mutation and risk of prostate cancer. Our group has developed the Yale School of Medicine Fusion Prostate Biopsy Program. This program uses cutting-edge multiparametric magnetic resonance imaging (MRI) to identify previously invisible lesions in the prostate. The office-based Artemis platform (Eigen, Grass Valley CA) then “fuses” these images with 3D ultrasound to achieve more precise and accurate prostate biopsies, allowing for better clinical staging with a single biopsy. The Yale Fusion Prostate Biopsy Program has dramatically improved prostate cancer detection to more than 60%, almost twice that of the current standard of care. Through the Yale Cancer Center Genetic Counseling program, which provides genetic counseling and testing to people at increased risk for hereditary cancer, we have an established cohort of families with known genetic mutations including BRCA2.

Our study, by combining the Fusion Prostate Biopsy Program and the Genetic Counseling program to perform highly sensitive prostate biopsies in a population of BRCA2 mutation carriers, is a novel approach to accurately determine the risk of prostate cancer, adverse pathologic features and abnormal MRI findings among BRCA2 mutation carriers. While it is beyond the scope of this pilot grant, we believe that early identification of men with higher risk disease should allow for more rapid treatment and a higher likelihood of cure. We hypothesize that the BRCA-2 mutation is associated with a higher risk of prostate cancer incidence, worse grade, and abnormal MRI findings compared to patients without this mutation. To address these important questions, our specific aims are:

1. To prospectively determine the incidence of prostate cancer in BRCA2 mutation carriers.
2. To investigate different characteristics of MRI-detected prostate lesions.
3. To compare pathologic and clinical findings to clinically matched controls using the same sensitive MRI-based biopsy technique.

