4. Localized prostate cancer is treatable and often curable while metastatic disease is not, hence prostate cancer screening is performed to identify patients at an earlier stage. Early detection of prostate cancer in this group of younger men at high-risk population may allow for identification while at a lower stage and grade, potentially increasing the number of patients able to receive treatment with curative intent.

All previous studies in the literature have evaluated the incidence of BRCA2 mutation carriers in a population of patients already diagnosed with prostate cancer. The incidence of prostate cancer in men with a BRCA2 mutation, however, has not been previously described.

3. **Research Plan:** Summarize the study design and research procedures using non-technical language that can be readily understood by someone outside the discipline. Be sure to distinguish between standard of care vs. research procedures when applicable, and include any flowcharts of visits specifying their individual times and lengths. Describe the setting in which the research will take place.

This is a cohort screening study to prospectively identify the incidence of prostate cancer in a population of BRCA2 carriers. All men identified to have a BRCA2 mutation as part of the Yale Cancer Genetic Counseling Program will be approached and offered participation in the study via our program newsletter, BRCA listserv, Facebook page and a targeted mailing. We will also contact all female BRCA2 carriers and ask them to invite their male relatives known to carry BRCA2 mutations into this study through the same means. For patients who test positive for a BRCA2 mutation after this study has opened, we will discuss this study with them at result disclosure and include it as part of their summary letter.

Potential participants will meet with a urologic oncologist to discuss the risks and benefits of prostate cancer screening including individual risks and benefits of PSA testing, prostate examination, pelvic MRI, prostate biopsy, and a prostate cancer diagnosis..

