Standard of care screening at the Yale Cancer Center for men with a normal prostate cancer risk consists of a PSA test and prostate physical examination beginning at age 50 years and if either is abnormal an MRI of the prostate followed by Fusion-targeted biopsy of the prostate is performed (Figures 1 and 2). Men with genetic risk factors such as African American or Caribbean heritage, a positive family history of prostate cancer, or a BRCA2 mutation, are counseled about their increased risk of prostate cancer and that prostate cancer screening (PSA and prostate exam then MRI and prostate biopsy if indicated) should begin at age 40yr but is available to them at any age.

Study participants will be identified because of their BRCA2 mutation that places them at increased risk for developing prostate cancer. Because this is a pre-selected high-risk population, and our goal is to establish the incidence of cancer and association of risk factors with developing disease, all men ≥ 30 years of age, able to give informed consent, and with at least a 5-10 year life expectancy will have PSA testing, prostate examination, Pelvic MRI, and Artemis fusion prostate biopsy (Figures 1 and 2).

Men identified to have prostate cancer will be treated according to current standards of care. Treatment for prostate cancer at the Yale Cancer Center is largely based on clinical risk; options include, but are not limited to, active surveillance for appropriate men with low risk disease, treatment with curative intent for men with localized intermediate and high risk prostate cancer, and systemic therapy for men with metastatic disease.

[figure not shown]

Figure 1. Instrument set up at Yale to perform precision imaging-guided biopsy. The prototype device of Artemis 3D biopsy tracking system. Instrument set up at Yale from Eigen (510K approved).

[figure not shown]
[figure not shown]

Figure 2. Precision image-guided biopsy. A+B) Identification of suspicious regions in two MRI sequences C) overlay of MR contoured region on realtime US view D+E) two planes of view of the 3D model generated by US and MR segmentation F) matching whole mount histology slide following prostatectomy.

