Typical clinical workflow for an Artemis MR-US fusion biopsy includes a pre-procedure MRI followed by a 12-core transrectal-ultrasound (TRUS) guided biopsy (Figure 1,2). The ultrasound transducer is fixed with a needle guide, and the biopsy needle is then guided to specific regions in the prostate gland for systematic sampling of the gland. If any areas suspicious for cancer (labeled regions of interest (ROIs)) are identified in the MRI, they are outlined using specialized software, and the target is visible on the Artemis device. Targeted biopsies will be taken from each ROI to rule out cancer in these suspicious areas.

4. **Genetic Testing** N/A

5. **Subject Population:** Provide a detailed description of the types of human subjects who will be recruited into this study.

Men \geq 30 years of age with known BRCA2 mutation and able to give informed consent.

6. **Subject classification:** Check off all classifications of subjects that will be specifically recruited for enrollment in the research project. Will subjects who may require additional safeguards or other considerations be enrolled in the study? If so, identify the population of subjects requiring special safeguards and provide a justification for their involvement.

 Children	 Healthy	 Fetal material, placenta, or dead fetus
 Non-English Speaking	 Prisoners	 Economically disadvantaged persons
 Decisionally Impaired	 Employees	 Pregnant women and/or fetuses
 Yale Students	 Females of childbearing potential	

NOTE: Is this research proposal designed to enroll children who are wards of the state as potential subjects? Yes No (If yes, see Instructions section VII #4 for further requirements)

7. **Inclusion/Exclusion Criteria:** What are the criteria used to determine subject inclusion or exclusion?

All men \geq 30 years of age with at least a ten-year life expectancy, a known BRCA2 mutation, ability to have an MRI, and able to give informed consent will be approached to participate in the study. If a man has received or is currently receiving treatment for prostate cancer he will be excluded from the study.

8. How will **eligibility** be determined, and by whom?

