11. Data and Safety Monitoring Plan: Include an appropriate Data and Safety Monitoring Plan (DSMP) based on the investigator's risk assessment stated below. (Note: the HIC will make the final determination of the risk to subjects.) For more information, see the Instructions, page 24.

a. What is the investigator's assessment of the overall risk level for subjects participating in this study?

- Moderate risk: participants will be offered the standard of care fusion targeted prostate biopsy that is performed at Yale and offered to other patients at risk for prostate cancer. Some participants, however, would not have received a biopsy if not participating in the study.

1. Personnel responsible for the safety review and its frequency:

The principal investigator will be responsible for monitoring the data, assuring protocol compliance, and conducting the safety reviews at the specified frequency which must be conducted at a minimum of every 6 months (including when reapproval of the protocol is sought). During the review process, the principal investigator (monitor) will evaluate whether the study should continue unchanged, require modification/amendment, or close to enrollment. Either the principal investigator, the IRB or the Yale Cancer Center Data and Safety Monitoring Committee (DSMC) have the authority to stop or suspend the study or require modifications.

2. The risks associated with the current study are deemed moderate for the following reasons: (choose those that apply)

1. We do not view the risks associated with the prostate biopsy as minimal given the alternative is no biopsy.
2. Given the now established safety and validity of the current biopsy procedure in our prior work, we do not view the proposed studies as high risk.

Although we have assessed the proposed study as one of moderate risk, the potential exists for anticipated and/or unanticipated adverse events, serious or otherwise, to occur since it is not possible to predict with certainty the absolute risk in any given individual or in advance of first-hand experience with the proposed study methods. Therefore, we provide a plan for monitoring the data and safety of the proposed study as follows:

3. Attribution of Adverse Events:

Adverse events will be monitored for each subject participating in the study and attributed to the study procedures / design by the principal investigator [name] according to the following categories:

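### The lead aim is called incidence, but the protocol describes one round of screening per man and no follow-up, so as written it estimates prevalence at the study screen

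*Combined protocol and SAP*

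**What the plan says.** **The target.** Section V.1 gives the single aim as "Determine the incidence of prostate cancer in men with the BRCA2 gene mutation as an independent indicator for prostate cancer screening". V.2 repeats incidence in its hypothesis and in aim 1, V.3 repeats it in the design sentence ("This is a cohort screening study to prospectively identify the incidence of prostate cancer in a population of BRCA2 carriers") and the stated goal, and V.12 uses it again.

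**The procedures.** V.3 says that all eligible men aged 30 or over "will have PSA testing, prostate examination, Pelvic MRI, and Artemis fusion prostate biopsy". It then says that men found to have cancer go on to standard care. It says nothing about what the study does next with men whose biopsy is negative. Section II.2 gives the project duration only as ongoing.

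**Entry.** V.7 reads: "If a man has received or is currently receiving treatment for prostate cancer he will be excluded from the study". Earlier PSA tests, MRI or negative biopsies are not exclusions.

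**How usual care differs.** For normal-risk men at the centre, PSA and examination come first, and "if either is abnormal an MRI of the prostate followed by Fusion-targeted biopsy of the prostate is performed". V.11 accepts the consequence: "Some participants, however, would not have received a biopsy if not participating in the study".

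**Comparison.** Aim 3 in V.2 is "To compare pathologic and clinical findings to clinically matched controls using the same sensitive MRI-based biopsy technique". The matching variables, and the reason the controls were biopsied, are not given. V.12 cites a detection range of 0.01 to 6.5% for normal-risk men in their 30s to 60s, without a time unit.

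**The concern.** An incidence rate counts new cases arising over time in people known to be free of disease at the start. It needs a disease-free baseline, follow-up and a person-time denominator, and the protocol specifies none of these. A cancer found at the study biopsy was already present when the man entered.

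A figure published as incidence would be read as the rate at which carriers develop cancer. V.1 ties the result to using the mutation as an independent reason to screen, so the label bears on how the result would be used.

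Who is biopsied also differs from usual care. That affects any comparison with population figures and, depending on how the controls were chosen, the cancer-yield part of aim 3. Either could seem to support or refute a higher risk in carriers because of who was biopsied.

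**Working it through.** The protocol states no expected number of cancers, interval or rate, so there is no figure of its own to reproduce. The yields below are assumed for illustration.

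**1. What can be computed.** Rate = new cases / person-years at risk after a cancer-free baseline. As written, person-years after the screen = 0, so the rate is undefined. Proportion = cancers found / men biopsied, and this can be computed.

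**2. Whether the proportion can be turned into a rate.** Under a steady state, I = P / [(1 − P) × D], where P is the prevalence and D the mean time for which a cancer is detectable but undiagnosed. The documents give no D. With P = 0.20, P/(1 − P) = 0.25:

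| Assumed D (years) | I per 1,000 person-years |
|---|---|
| 2 | 125 |
| 5 | 50 |
| 10 | 25 |
| 15 | 16.7 |

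The same data give answers 7.5-fold apart (125/16.7).

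**3. Precision of the proportion.** Exact (Clopper–Pearson) 95% limits: lower = the 2.5% point of Beta(x, n − x + 1), upper = the 97.5% point of Beta(x + 1, n − x).

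| Assumed result | Estimate | 95% CI |
|---|---|---|
| 5/100 | 5.0% | 1.6–11.3% |
| 10/100 | 10.0% | 4.9–17.6% |
| 20/100 | 20.0% | 12.7–29.2% |
| 2/25 (one of four equal age groups) | 8.0% | 1.0–26.0% |
| 10/80 (80 of 100 enrolled men biopsied) | 12.5% | 6.2–21.8% |

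The last row shows why the denominator must be stated: ten cancers are 10.0% of 100 men enrolled but 12.5% of 80 men biopsied.

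**4. Effect of biopsying everyone.** Let f (below 1) be the share of men with an abnormal PSA or examination, p1 the detection proportion in them, and p0 that in the rest. Suppose the mutation has no effect.

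- Biopsy everyone: yield per man = f·p1 + (1 − f)·p0.
- Biopsy only after an abnormal test: yield per man = f·p1, which is lower whenever p0 > 0.
- The same policy, counted per man biopsied: yield = p1, which is higher whenever p0 < p1.

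So biopsying everyone raises the yield against a population-type figure and lowers it against controls biopsied for cause. Comparing p1 with p1, or everyone with everyone, removes the problem. The documents give no values for f, p1 or p0, so I put no size on this.

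**5. What a real rate would cost in precision.** 100 men give at most 100 person-years per year of follow-up. One new cancer in 100 person-years is 1.0 per 100, with exact Poisson 95% limits of 0.03 to 5.6. A longer illustration removes 20% as prevalent cases and assumes 20 per 1,000 person-years over five years: 80 × (1 − e^(−0.1)) / 0.02 = 381 person-years and 381 × 0.02 = 7.6 expected cancers. With 8 observed, the interval is about 9 to 41 per 1,000.

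**The case against.** **Follow-up may be intended.** The protocol never says that each man is screened only once. It calls the study a prospective cohort, describes the project as ongoing, and plans an initial evaluation of 100 men. The consent form that Section VII.11 says is attached is not in the text available here. A reader might infer that the protocol rules out later rounds, and the documents do not support that. What stands is narrower: the protocol text specifies no follow-up, and those words supply no schedule, denominator or analysis. By their captions, the two missing figures show equipment and biopsy images, not visits.

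**The word is used loosely.** The end of V.2 uses incidence for the share of diagnosed patients who carry the mutation, where it can only mean a proportion, and V.12 speaks of detection. V.2 also calls the work a pilot. That is fair, and it makes this largely a matter of labelling. It does not make the label safe for a reader who sees only the result.

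**The benchmarks are not planned comparators.** A reader might set the yield against the 0.01–6.5% in V.12, or against the fusion program's claim in V.2 to have "dramatically improved prostate cancer detection to more than 60%, almost twice that of the current standard of care". No section plans either comparison. The first is background to the choice of 100 men, and the second describes the biopsy program. Ratios to them would not measure harm to a planned analysis.

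**Aim 3 may be sound.** The controls are to be clinically matched, and matching might include PSA. Every carrier has PSA and examination results, so a like-for-like comparison is possible even if the controls were biopsied for cause. The documents do not show that aim 3 is invalid. They leave its basis unstated.

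**Conclusion.** The concern holds, limited to the protocol as written. It names incidence as its target and describes a study that yields the prevalence of biopsy-detected cancer at the study screen. Post-screen person-time is zero, so no rate can be calculated, and converting the proportion needs a duration that the documents do not give. This rests on reading one listing of procedures, with no repeat or interval, as one round.

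Two stronger readings should be avoided. The study screen should not be called a first screen: V.3 says screening is available to carriers at any age and advised from 40, and V.7 does not exclude men already screened, so some participants may have been. Nor are the data without value: a detection proportion with a sound interval and denominator is useful. The point should be fixed because it changes what the trial may conclude, but it does not require a change in conduct.

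**What to change.** - In V.1, V.2, V.3 and V.12, replace incidence, where it names the study's own target, with the prevalence (detection proportion) of biopsy-detected prostate cancer at the study screen.
- Report it with an exact 95% interval. Use men who completed the study biopsy as the denominator, and show the number enrolled but not biopsied.
- Tabulate it by age group, and by prior screening or biopsy where the medical record gives this.
- State that it is not an incidence rate and is not directly comparable with population figures such as the 0.01–6.5% in V.12, because every participant is to be biopsied.
- For aim 3, read a difference in cancer yield as an effect of the mutation only where carriers and controls came to biopsy on a comparable basis: either all biopsied regardless of PSA or examination, or compared within, or matched on, those results. Otherwise call it descriptive.

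The cost is wording in four sections and tabulations from the medical-record data. The study gives up the claim to an incidence, age-group intervals will be wide, and the yield comparison in aim 3 may end up descriptive. If a rate of new disease is what is wanted, the protocol must define a cancer-free baseline, follow-up and person-time. That is a design change beyond this fix, and with 100 men the rate would still be imprecise.

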Yale genetic counselors will determine initial eligibility from the BRCA2 registry to confirm the presence of a BRCA2 mutation. Trained physicians will determine clinical eligibility based on medical history.

9. **Risks:** Describe the reasonably foreseeable risks, including risks to subject privacy, discomforts, or inconveniences associated with subjects participating in the research.

Risks of prostate biopsy include: infection, rectal bleeding, blood in urine or semen, prostatitis, urosepsis, urinary retention, and potential difficulty with urination.

Magnetic resonance (MR) is a technique that uses magnetism and radio waves, not x-rays, to take pictures and measure chemicals of various parts of the body. The United States Food and Drug Administration (FDA) has set guidelines for magnet strength and exposure to radio waves, and we carefully observe those guidelines.

Patients will be watched closely throughout the MR study. Some people may feel uncomfortable or anxious. If this happens to you, you may ask to stop the study at any time and we will take you out of the MR scanner. On rare occasions, some people might feel dizzy, get an upset stomach, have a metallic taste or feel tingling sensations or muscle twitches. These sensations usually go away quickly but please tell the research staff if you have them.

There are some risks with an MR study for certain people. If someone has a pacemaker or some metal objects inside their body, they may not be in this study because the strong magnets in the MR scanner might harm them. Another risk is a metallic object flying through the air toward the magnet and hitting the participant. To reduce this risk we require that all people involved with the study remove all metal from their clothing and all metal objects from their pockets. Nothing metal can be brought into the magnet room at any time. Also, once the participant is in the magnet, the door to the room will be closed so that no one from outside accidentally goes near the magnet.

10. Minimizing Risks: Describe the manner in which the above-mentioned risks will be minimized.

Risks will be minimized using standard of care methods to limit prostate biopsy-related patient discomfort and the risk of infection through administration of local anesthetic and peri-procedure antibiotics, respectively.

FDA guidelines for MRI safety are strictly adhered to.

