7. Plan for reporting adverse events to co-investigators on the study, as appropriate the protocol's research monitor(s), e.g Yale Cancer Center Data and Safety Monitoring Committee (DSMC), Protocol Review Committee (PRC), DSMBs, study sponsors, funding and regulatory agencies, and regulatory and decision-making bodies.

For the current study, the following individuals, funding, and/or regulatory agencies will be notified (choose those that apply):

All Co-Investigators listed on the protocol.

Yale Cancer Center Data and Safety Monitoring Committee (DSMC)

National Institutes of Health

Food and Drug Administration (Physician-Sponsored IND # _____)

Medical Research Foundation (Grant _____)

The principal investigator [name] will conduct a review of all adverse events upon completion of every study subject. The principal investigator will evaluate the frequency and

severity of the adverse events and determine if modifications to the protocol or consent form are required.

d. For multi-site studies for which the Yale PI serves as the lead investigator: N/A

12. Statistical Considerations: Describe the statistical analyses that support the study design.

This is a screening study to establish the incidence of prostate cancer in a high-risk population since it is not currently known. There is an estimated 4.6-23 fold increased risk of prostate cancer, especially in men < 58 years of age with a BRCA2 mutation. Typically, prostate cancer detection in normal risk men correlates directly with age and ranges between 0.01 and 6.5% for men in their 30s-60s (CDC website). Given these parameters, we plan initial evaluation of 100 men.

SECTION VI: RESEARCH INVOLVING DRUGS, BIOLOGICS, RADIOTRACERS, PLACEBOS AND DEVICES

N/A

SECTION VII: RECRUITMENT/CONSENT AND ASSENT PROCEDURES

1. Targeted Enrollment: Give the number of subjects:

- a. targeted for enrollment at Yale for this protocol 100
- b. If this is a multi-site study, give the total number of subjects targeted across all sites

2. Indicate recruitment methods below. Attach copies of any recruitment materials that will be used.

 Flyers	 Internet/Web Postings	 Radio
 Posters	 Mass E-mail Solicitation	 Telephone

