- ii. If requesting a waiver of **signed** authorization, describe why it would be impracticable to obtain the subject's signed authorization for use/disclosure of this data;

By signing this protocol application, the investigator assures that the protected health information for which a Waiver of Authorization has been requested will not be reused or disclosed to any person or entity other than those listed in this application, except as required by law, for authorized oversight of this research study, or as specifically approved for use in another study by an IRB.

Researchers are reminded that unauthorized disclosures of PHI to individuals outside of the Yale HIPAA-Covered entity must be accounted for in the “accounting for disclosures log”, by subject name, purpose, date, recipients, and a description of information provided. Logs are to be forwarded to the Deputy HIPAA Privacy Officer.

7. **Required HIPAA Authorization:** If the research involves the creation, use or disclosure of protected health information (PHI), separate subject authorization is required under the HIPAA Privacy Rule. Indicate which of the following forms are being provided:

Compound Consent and Authorization form
 HIPAA Research Authorization Form

8. **Consent Personnel:** List the names of all members of the research team who will be obtaining consent/assent.

[name]

9. Process of Consent/Assent: Describe the setting and conditions under which consent/assent will be obtained, including parental permission or surrogate permission and the steps taken to ensure subjects' independent decision-making.

Prior to screening for prostate cancer patients will have an office visit as part of standard clinical care to discuss the risks and benefits of prostate cancer screening. During this visit, if they are interested in being screened for prostate cancer and meet eligibility criteria the study will be described and if patients are interested in participating they will be provided a study information sheet and asked to sign consent. Only patients that can provide written informed consent will be enrolled in this study, and if there is any doubt subjects will not be enrolled. Information sheets will also be available to patients as part of the Yale Cancer Genetic Counseling Program.

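### The exclusion is keyed to treatment rather than diagnosis, so a carrier with known but untreated prostate cancer can enrol and inflate the incidence estimate

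*Combined protocol and SAP*

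**What the plan says.** Section V.7 gives the inclusion criteria as age 30 or over, a life expectancy of at least ten years, a known BRCA2 mutation, ability to have an MRI and capacity to consent. It then gives one exclusion: "If a man has received or is currently receiving treatment for prostate cancer he will be excluded from the study". The population statement in Section V.5 adds no condition about prior diagnosis.

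Four other places bear on who can enter:

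- **Recruitment (Section V.3):** "All men identified to have a BRCA2 mutation as part of the Yale Cancer Genetic Counseling Program will be approached". The frame is all male carriers known to the programme, not only undiagnosed ones.
- **Eligibility decision (Section V.8):** genetic counsellors confirm the mutation, and "Trained physicians will determine clinical eligibility based on medical history". No rule on prior diagnosis is given for them to apply.
- **Consent (Section VII.9):** the study is described to men "if they are interested in being screened for prostate cancer and meet eligibility criteria", which leads back to Section V.7.
- **Treatment (Section V.3):** the options listed for men found to have cancer include "active surveillance for appropriate men with low risk disease".

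The statistical section (V.12) sets 100 men as the initial number. It does not define a case or say how a previously known cancer is handled.

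**The concern.** The first aim is the incidence of prostate cancer in carriers, estimated prospectively in a screening cohort. Section V.2 sets the study apart from earlier work on this ground: "All previous studies in the literature have evaluated the incidence of BRCA2 mutation carriers in a population of patients already diagnosed with prostate cancer". A man whose cancer is already known is not at risk of a first diagnosis. If he enrols and is counted, he enters as a case that screening did not find, and the study takes on part of the limitation it was designed to avoid.

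The same man would also enter the MRI description and the comparison with matched controls in the further aims of Section V.2. The resulting error would not show in a confidence interval, because the interval reflects sampling variation only.

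**Working it through.** **Step 1. Is there a gap in the text?** Take a carrier aged 30 or over, diagnosed at an earlier biopsy, with no treatment started. He passes each inclusion criterion in V.7 and is not caught by the exclusion. V.5, V.8, VII.9 and V.12 add nothing that would remove him. For a man on active surveillance the text is ambiguous: V.3 lists surveillance among the treatment options, so he may count as receiving treatment, but V.7 does not say so.

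**Step 2. Inputs for the size.**

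- N = 100 (V.12). The document gives no formula, precision target or power for this number, so there is no planned figure to reproduce.
- k, the number of known cases enrolled and counted: not in the documents. Assumed 0, 1, 2 and 5.
- p, the detection rate in the other men: not in the documents. Assumed 5%, 10% and 30%.
- V.12 says detection in normal-risk men "ranges between 0.01 and 6.5% for men in their 30s-60s", and "There is an estimated 4.6-23 fold increased risk of prostate cancer". The upper baseline times the lower multiplier is 6.5% × 4.6 = 29.9%, which is the reason for the illustrative 30%. The document does not form this product itself. The upper multiplier cannot be used with that baseline, since 6.5% × 23 = 149.5%.
- Every known case is assumed to be counted as a detected cancer.

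**Step 3. Formula.** Estimate = (k + (100 − k) × p) / 100. Subtracting p gives bias = (k/100) × (1 − p), that is, k × (1 − p) percentage points. This is positive for every k > 0 and p < 1.

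**Step 4. Results.** For example, k = 5 and p = 5% gives (5 + 95 × 0.05)/100 = 9.75/100 = 9.75%.

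| p in other men | k = 0 | k = 1 | k = 2 | k = 5 | bias at k = 5 |
|---|---|---|---|---|---|
| 5% | 5.0% | 5.95% | 6.9% | 9.75% | 4.75 points |
| 10% | 10.0% | 10.9% | 11.8% | 14.5% | 4.5 points |
| 30% | 30.0% | 30.7% | 31.4% | 33.5% | 3.5 points |

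**Step 5. Scale.** Exact (Clopper-Pearson) 95% intervals at N = 100 are 1.6% to 11.3% for 5 cancers, 4.9% to 17.6% for 10, and 21.2% to 40.0% for 30. One known case shifts the estimate by 0.7 to 0.95 points, far inside these intervals. Five shift it by 3.5 to 4.75 points, still inside them, but at p = 5% that nearly doubles the estimate (9.75/5 = 1.95).

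**Step 6. After the change.** With prior diagnoses excluded, k = 0 and the estimate has expectation p, so this bias vanishes.

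**The case against.** The strongest reply is that the whole protocol describes screening of undiagnosed men. A urologic oncologist counsels each man on what a diagnosis would mean (V.3), the risk assessment takes no biopsy as the alternative (V.11), and the expected benefit is earlier discovery (Section IX). For bias to arise, a man with known cancer must pass that consultation and a physician's history review, and then be counted. If surveillance is read as treatment, the largest obvious untreated group is already out. No text says that known cancers will be counted, and the word incidence itself argues against counting them. The direction also depends on the target: if the quantity were cancer present among untreated carriers, counting a known case would not be an upward error. Finally, k and p are both assumed.

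Much of this stands. Such enrolment is unlikely, no such man is shown to exist in the programme, and the size is hypothetical. But none of the passages cited is an eligibility criterion. The protocol does write an exclusion about prostate cancer history and ties it to treatment, so a physician applying it literally has no stated ground to turn away an untreated man, and two physicians could decide differently. The stated aim is incidence, and for that aim the direction is upward. Reading the target as prevalence would not rescue the rule either, since it drops diagnosed men who were treated and keeps those who were not.

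**Conclusion.** The concern holds. As written, Section V.7 admits men with known, untreated prostate cancer to a study of incidence, and no other section removes them from the cohort or from the count. If k are enrolled and counted among 100, the estimate is too high by k × (1 − p) points: just under one point per man at p = 5%, and 3.5 to 4.75 points for five men over p = 30% down to 5%. With k = 0 there is no bias.

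The defect in the criterion is certain; the bias is only possible. It rests on such men enrolling and being counted, and on assumed values of k and p. The point should be fixed because it touches the primary estimate and is easily prevented. It does not invalidate the design.

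**What to change.** 1. In V.7, replace the exclusion with: any prostate cancer diagnosis before enrolment, treated or not, including men on active surveillance.
2. In V.12, add a counting rule: only cancers first diagnosed by the study biopsy enter the primary numerator.
3. If a previously diagnosed man has already been enrolled, remove him from both numerator and denominator of the primary estimate and report him separately.

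The cost is one sentence in each of two sections and one question within the history review that V.8 already requires. Any previously diagnosed volunteer becomes ineligible.

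A separate consistency point, which carries no weight in this conclusion: V.3 states a minimum life expectancy of 5 to 10 years and V.7 states ten. The two should be reconciled.
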